5.3.1. Plasma Pharmacokinetic Parameters

Actual PK sampling times will be used in the derivation of plasma PK parameters.

If a PK parameter cannot be derived from a participant's concentration data, the parameter will be coded as NC (i.e. not calculated). (Note that NC values will not be generated beyond the day that a participant discontinues.)

In summary tables, statistics will be calculated by setting NC values to missing; and statistics will be presented for a particular treatment group/analyte with ≥ 3 evaluable measurements. For statistical analyses (i.e. mixed effect model), PK parameters coded as NC will also be set to missing; and analyses will not be performed for a particular parameter if more than 50% of the data are NC.

If an individual participant has a known biased estimate of a plasma PK parameter (due for example to an unexpected event such as vomiting before all the compound is adequately absorbed in the body), this will be footnoted in summary tables and will not be included in the calculation of summary statistics or statistical analyses.

6. ANALYSES AND SUMMARIES

Unless otherwise stated, all analyses, summaries and listings will be produced by group (as outlined in Section 5) which would include all 4 groups in the same analysis/output.

6.1. Primary Endpoint(s)

6.1.1. C_{max} , AUC_{inf} , AUC_{last} , fu for PF-06882961

6.1.1.1. Main Analysis

C_{max} , AUC_{inf} (if data permit), AUC_{last} and fu will be listed, summarized descriptively and analyzed by group for participants in the PK parameter set (as defined in Section 4). Missing values will be handled as detailed in Section 5.3.1.

A one-way analysis of variance (ANOVA) described in Section 5.2.3, that includes all 4 groups in the same model, will be used to compare the natural log transformed of C_{max} , AUC_{inf} , AUC_{last} and fu of PF-06882961 separately, for each of the hepatic impairment groups (Test, Groups 2, 3, 4) to the healthy normal hepatic function group (Reference, Group 1).

For summary statistics and median or mean plots by sampling time, the nominal PK sampling time will be used. For individual participant plots by time, the actual PK sampling time will be used. The plasma PK parameters of PF-06882961 for each group will be summarized as specified in Table 6 below.

Table 6. Summary statistics to be produced for Plasma PK Parameters of PF-06882961

Parameter	Summary Statistics
------------------	---------------------------

C_{max} , AUC_{inf} (if data permit), AUC_{last} and fu	N, arithmetic mean, median, $cv\%$, standard deviation, minimum, maximum, geometric mean and geometric $cv\%$.
--	--

Supporting data from the estimation of $t_{1/2}$ will be listed by group: terminal phase rate constant (k_{el}); goodness of fit statistic from the log-linear regression (r^2); the percent of AUC_{inf} based on extrapolation ($AUC_{extrap\%}$); and the first, last, and number of time points used in the estimation of k_{el} . This data may be included in the clinical study report.

The following plot will be presented:

- Box and whisker plots for individual PK parameters (AUC_{inf} , AUC_{last} , C_{max} and fu) will be constructed by group and overlaid with geometric means.

6.1.1.2. Exploratory/Supplementary Analysis

Exploratory analysis using linear regression will be used to analyze the potential relationship between appropriate PK parameters [eg, AUC_{inf} , AUC_{last} , C_{max} and fu] and hepatic function (eg, serum albumin concentration, prothrombin time or total bilirubin), as described in Section 5.2.3.

Plots of PK parameters (eg, AUC_{inf} , AUC_{last} , C_{max} and fu) versus hepatic function (e.g. serum albumin, prothrombin time or total bilirubin, plotted separately) will be constructed, with a regression line and 90% confidence region included from the main linear regression model.

6.2. Secondary Endpoint(s)

Any clinical laboratory, ECG, BP, and pulse rate abnormalities of potential clinical concern will be described.

No formal analyses are planned for safety data.

The safety endpoints detailed in Section 3.2 will be listed and summarized in accordance with sponsor reporting standards based on the safety population (as defined in Section 4), with more details provided below.

6.2.1. Adverse Events

Adverse events will be summarised by group and overall, in accordance with sponsor reporting standards using the safety population defined in Section 4.

If applicable, subject discontinuations due to adverse events will be detailed and summarized.

6.2.2. Laboratory Data

Laboratory data will be listed and summarized by group and overall, in accordance with the sponsor reporting standards using the safety population defined in Section 4. Baseline is as defined in Section 3.2.

6.2.3. Vital Signs

Absolute values and changes from baseline in seated systolic and diastolic blood pressure and pulse rate will be summarised by group, according to sponsor reporting standards using the safety population defined in Section 4. Baseline is as defined in Section 3.2.

Maximum and minimum absolute values and maximum changes from baseline for seated vital signs will also be summarised descriptively by group using categories as defined in Appendix 2. Numbers and percentages of participants meeting the categorical criteria will be provided. All planned and unplanned post dose time points will be counted in these categorical summaries. All values meeting the criteria of potential clinical concern will be listed.

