### **5.2.3. Additional Exclusion Criteria for Participants with Impaired Hepatic Function (Cohorts 2, 3, and 4 Only)**

Participants presenting with any of the following will **not** be included in the study:

1. Hepatic carcinoma **or** hepatorenal syndrome **or** limited predicted life expectancy (defined as less than 1 year in Cohorts 2 & 3 and less than 6 months for Cohort 4 only);
2. A diagnosis of hepatic dysfunction secondary to any acute ongoing hepatocellular process that is documented by medical history, physical examination, liver biopsy, hepatic ultrasound, computerized tomography scan, or magnetic resonance imaging (MRI);
3. History of surgery that would be expected to alter absorption, distribution, metabolism, or excretion (ADME) properties of PF-06882961 (eg, status post porta-caval shunt surgery);

**NOTE:** Participants with a transjugular intrahepatic portosystemic shunt (TIPS) are permitted provided that they meet the Child-Pugh criteria;

4. History of gastrointestinal hemorrhage due to esophageal varices or peptic ulcers less than **4 weeks** prior to Screening;
5. Signs of clinically active Grade 3 or 4 hepatic encephalopathy (ie, >Grade 2 Portal Systemic Encephalopathy score; refer to [Appendix 8](#));
6. Severe ascites and/or pleural effusion, except for those categorized in Cohort 4 who may be enrolled provided participant is medically stable, per the investigators' medical judgment;
7. Participants who have previously received a kidney, liver, or heart transplant;
8. Screening **supine** 12-lead ECG demonstrating a QTcF interval >470 msec or a QRS interval >120 msec. If QTcF exceeds 470 msec, or QRS exceeds 120 msec, the ECG should be repeated 2 more times and the average of the 3 QTcF or QRS values should be used to determine eligibility;
9. At screening, persistent severe, uncontrolled hypertension; for example: **seated** SBP  $\geq 180$  mm Hg and/or DBP  $\geq 105$  mm Hg after  $\geq 5$ -minute of seated rest, with a single repeat permitted to assess eligibility, if needed, at each of these 2 visits:
  - For participants with SBP  $\geq 160$  (and  $< 179$ ) mm Hg **or** DBP  $\geq 100$  (and  $< 104$ ) mm Hg, the period between Screening and Day -1 must be used to refine the doses of the agents used for management of BP with the aim to have stable BP by Day 1 [refer to [Section 5.2.4](#)];

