#### **5.2.4. Criteria for Dosing on Day 1**

Participants will progress to dosing on Day 1 provided they have satisfied all the following criteria:

- Breath alcohol test, using kits provided by sponsor-identified central laboratory, on Day -1 is negative;
- In women of childbearing potential, urine pregnancy test on Day -1 is negative as reported by on-site pregnancy test using supplies provided by the sponsor-identified central laboratory;
- Safety-related laboratory tests collected and analyzed by sites' local laboratory on Day -1, **if performed** at investigator discretion, upon review on Day 1 must reflect the participant to be in stable medical condition;
- **Cohort 1 and Cohort 2 only:** Approval from the sponsor must be obtained before proceeding with dosing participants in either Cohort 1 or Cohort 2;
- **Cohorts 2 and 3 only:** Participants must have measurement on Day 1 of SBP  $\leq 159$  mm Hg **and** DBP  $\leq 99$  mm Hg;
  - A single repeat assessment is permitted, to confirm that the above criterion is met [and in such cases, the repeat assessment overrides initial results];
- **Cohort 4 only:** Participants must have measurement on Day 1 of SBP  $\leq 159$  mm Hg **and** DBP  $\leq 105$  mm Hg;
  - A single repeat assessment is permitted, to confirm that the above criterion is met [and in such cases, the repeat assessment overrides initial results].

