Appendix 2. Categorical Classes for ECG and Vital Signs of Potential Clinical Concern

Categories for QTcF

Absolute value of QTcF (msec)	>450 and \leq 480	>480 and \leq 500	>500
Increase from baseline in QTcF (msec)	>30 and \leq 60	>60	

Categories for PR and QRS

PR (ms)	max. \geq 300	
PR (ms) increase from baseline	Baseline >200 and max. \geq 25% increase	Baseline \leq 200 and max. \geq 50% increase
QRS (ms)	max. \geq 140	
QRS (ms) increase from baseline	\geq 50% increase	

Categories for Vital Signs

Systolic BP (mm Hg)	min. <90	
Systolic BP (mm Hg) change from baseline	max. decrease \geq 30	max. increase \geq 30
Diastolic BP (mm Hg)	min. <50	
Diastolic BP (mm Hg) change from baseline	max. decrease \geq 20	max. increase \geq 20
Supine pulse rate (bpm)	min. <40	max. >120

Measurements that fulfill these criteria are to be listed in the report.

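### SAP Appendix 2 has no upper absolute blood-pressure class, so some high post-dose readings in participants dosed with a high baseline are neither counted nor flagged

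*SAP*

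**What the plan says.** SAP 6.2.3 plans a categorical summary of seated vital signs: "Maximum and minimum absolute values and maximum changes from baseline for seated vital signs will also be summarised descriptively by group using categories". Numbers and percentages of participants are to be given, planned and unplanned post-dose readings both count, and "All values meeting the criteria of potential clinical concern will be listed". SAP 6.2 adds: "Any clinical laboratory, ECG, BP, and pulse rate abnormalities of potential clinical concern will be described".

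SAP Appendix 2 supplies the categories:

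- SBP: minimum below 90; decrease or increase of 30 or more.
- DBP: minimum below 50; decrease or increase of 20 or more.
- Pulse rate: minimum below 40; maximum above 120.

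Only pulse rate has an upper absolute class. SAP 3.2 takes baseline as the last measurement before dosing.

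Two parts of the protocol bear on how high pressure may be. Section 5.2.4, in criteria that begin "Participants must have measurement on Day 1 of SBP", permits dosing in Cohorts 2 and 3 up to 159/99 mm Hg and in Cohort 4 up to 159/105. Section 5.2.3 excludes impaired participants with a condition worded "At screening, persistent severe, uncontrolled hypertension", and gives SBP of at least 180 and/or DBP of at least 105 as its example.

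**The concern.** Read literally, SAP 6.2.3 calls for a category on the maximum absolute value, and for blood pressure Appendix 2 has none to apply. The change classes stand in for it only when the rise is large. A participant who starts high needs a smaller rise to reach a high absolute reading, so the rule is least sensitive in the participants whose permitted baseline is highest. These are mainly Cohorts 2 to 4, whose safety is the secondary objective.

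SAP 6.2 does not close the gap when it promises to describe abnormalities of potential clinical concern, because Appendix 2 holds the only stated blood-pressure criteria for that term. The by-cohort table could show no high-pressure finding although such a reading occurred. In a cohort of 6, one participant is 1/6 = 16.7 percentage points. If Cohort 4 is cut to 4, one participant is 1/4 = 25 points.

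**Working it through.** The plan gives no figure to reproduce. The check is a count over whole mm Hg, the unit of recording in Protocol 8.2.2.

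**Inputs.** The increase classes are ≥30 (SBP) and ≥20 (DBP), from SAP Appendix 2. The Day 1 ceilings are 159/99 (Cohorts 2 and 3) and 159/105 (Cohort 4), from Protocol 5.2.4. Section 5.2.4 sets no Day 1 pressure ceiling for Cohort 1, so the screening limits in Protocol 5.2.2 (below 140 and below 90, hence 139/89) are assumed to hold at baseline. The reference figures 180 and 105 come from Protocol 5.2.3 and serve here only as a yardstick.

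**Highest reading that meets no class** = baseline ceiling + 29 (SBP) or + 19 (DBP).

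- SBP, Cohorts 2 to 4: 159 + 29 = 188.
- DBP, Cohorts 2 and 3: 99 + 19 = 118.
- DBP, Cohort 4: 105 + 19 = 124.
- Cohort 1: 139 + 29 = 168 and 89 + 19 = 108.

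**Baselines from which a reading at or above the yardstick can escape.** For SBP, baseline + 29 ≥ 180 gives baseline ≥ 151. For DBP, baseline + 19 ≥ 105 gives baseline ≥ 86.

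| Cohort | Highest unflagged SBP / DBP | Baselines, SBP ≥180 unflagged | Baselines, DBP ≥105 unflagged |
|---|---|---|---|
| 1 (assumed 139/89) | 168 / 108 | none | 86–89 |
| 2 and 3 | 188 / 118 | 151–159 | 86–99 |
| 4 | 188 / 124 | 151–159 | 86–105 |

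The systolic gap is narrow and confined to Cohorts 2 to 4. The diastolic gap is wider and touches every cohort.

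**Check of the fix.** With upper rows at 180 and 105 applied whatever the baseline, no baseline and post-dose pair at or above those figures escapes in any cohort. If the diastolic row were restricted to baselines below 105, a Cohort 4 participant going from 105 to 124 (+19) would still meet nothing. The restriction must therefore not govern the flag.

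**The case against.** **Few readings are at risk.** The Schedule of Activities appears to show one scheduled in-clinic post-dose blood pressure, at discharge at about 48 hours, although the extracted table is imperfectly aligned. Otherwise there are early termination and a follow-up that is by default a telephone contact. That is roughly 24 planned readings in the study. With the 5 to 7 hour half-life in Protocol 4.2, 48 hours is about 7 to 10 half-lives after a single dose (48/7 = 6.9; 48/5 = 9.6). This stands and limits the weight of the point, although unplanned readings also count under SAP 6.2.3.

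**The values are not lost.** SAP 6.2 lists the safety endpoints, and SAP 5.2.1 prints the group maximum, so a reading of 188 would be visible in a cohort of 6. Protocol Appendix 3 has clinically significant vital signs recorded as adverse events, and Protocol 9.4.2 has blood pressure reviewed during the study. The SAP also defers to sponsor reporting standards that are not in the documents. This stands too. A reader might infer that high readings would go unreported, and the documents do not support that.

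**No clear promise is broken.** The sentence in SAP 6.2.3 covers vital signs collectively, and pulse rate has no change class. Detecting high pressure by change is also defensible where baseline may already be high. This is fair as to wording. It does not alter the fact that a high absolute pressure has no criterion.

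**The 180/105 figures are a screening example.** They illustrate persistent hypertension, with a repeat permitted, and Protocol 5.2.4 itself allows Cohort 4 dosing at DBP 105. A reader might infer that the protocol would call a single unflagged reading severe hypertension. Such a reading matches the numbers but not the full description.

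**Conclusion.** The gap is real, and its limits follow from the documents' own numbers: post-dose readings up to 188/118, or DBP 124 in Cohort 4, can meet no class of potential clinical concern. These maxima assume the Day 1 ceilings are respected and need no assumption about variability. The Cohort 1 row assumes that screening limits carry over to baseline.

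The consequence is small. It concerns the count and the flag in a descriptive secondary summary; no decision rule depends on it (SAP 5.1), and the primary PK analysis is untouched.

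A reader might also want the share of high readings that would be missed. The documents give neither a within-person standard deviation for blood pressure nor an expected rise, and Protocol 2.2.2.1 reports no clear adverse trend in vital signs apart from heart rate increases. No such percentage is supported, and none is offered. The point is worth correcting because the correction costs almost nothing.

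**What to change.** In SAP Appendix 2, add one upper absolute row for SBP and one for DBP, and keep the existing change classes. The limits could be the 180 and 105 mm Hg already in Protocol 5.2.3, or others that the sponsor justifies. They would be reporting limits only and would trigger no clinical action.

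In SAP 6.2.3, list every post-dose value that meets the new rows, whatever the baseline, with the baseline alongside. Give the participant count by cohort twice: overall, and for those whose baseline was below the limit. At 180/105, and with the Day 1 ceilings respected, the two counts in Cohorts 2 to 4 can differ only through a Cohort 4 diastolic baseline of exactly 105.

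The cost is two table rows and a sentence in the SAP, with no new data and no protocol amendment. The downside is that some participants with pre-existing high pressure will be flagged after a modest change. At the ceilings, the smallest flagged systolic rise is 180 − 159 = 21 mm Hg. The smallest diastolic rise is 105 − 99 = 6 in Cohorts 2 and 3, and zero in Cohort 4. The listed baseline and the second count make this visible.

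The same edit can reconcile the pulse-rate label in Appendix 2, which says supine where SAP 6.2.3 and the protocol use seated measurements.

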6.2.4. ECG

Absolute values and changes from baseline in QT interval, heart rate, QTcF interval, PR interval and QRS interval will be summarised by group using sponsor reporting standards using the safety population defined in Section 4. Tables will be paged by parameter. Baseline is as defined in Section 3.2.

Maximum absolute values and changes from baseline for QTcF, PR and QRS will also be summarised descriptively by group using categories as defined in Appendix 2. Numbers and percentages of participants meeting the categorical criteria will be provided. All planned and unplanned post dose time points will be counted in these categorical summaries. All values meeting the criteria of potential clinical concern will be listed.

6.3. Other Endpoint(s)

6.3.1. Additional Plasma Pharmacokinetic Parameters of PF-06882961

$C_{max,u}$, $AUC_{inf,u}$, $AUC_{last,u}$, CL/F , CL_u/F , V_z/F , $V_{z,u}/F$, T_{max} , $t_{1/2}$ will be listed and summarized descriptively by group in the PK parameter set (as defined in Section 4). Missing values will be handled as detailed in Section 5.3.

The additional plasma PK parameters of PF-06882961 for each group will be summarized as specified in Table 7 below.

Table 7. Summary statistics to be produced for Additional Plasma PK Parameters of PF-06882961

Parameter	Summary Statistics
$C_{max,u}$, $AUC_{inf,u}$, $AUC_{last,u}$, CL/F , CL_u/F , V_z/F , $V_{z,u}/F$	N, arithmetic mean, median, cv%, standard deviation, minimum, maximum, geometric mean and geometric cv%.
T_{max}	N, median, minimum, maximum.
$t_{1/2}$	N, arithmetic mean, median, cv%, standard deviation, minimum, maximum.

The following plot will be presented:

- Box and whisker plots for individual PK parameters ($AUC_{inf,u}$, $AUC_{last,u}$ and $C_{max,u}$) will be constructed by group and overlaid with geometric means.

The following summaries will additionally be presented for the plasma concentration data of PF-06882961 using the PK Concentration Set (as defined in Section 4):

- a listing of all concentrations sorted by participant ID and nominal time post-dose for each group. The concentration listing will also include the actual times. Deviations from the nominal time will be given in a separate listing.
- a summary of concentrations for each nominal time post-dose (produced separately for each group), where the set of statistics will include n, mean, median, standard deviation, coefficient of variation (cv), minimum, maximum and the number of concentrations above the lower limit of quantification.
- median concentration time plots (on both linear and semi-log scales) against nominal time post-dose by group in the same plot.
- individual concentration time plots by group (on both linear and semi-log scales) against actual time post-dose (there will be separate spaghetti plots for each group, with a line for each participant, per scale).

The nominal PK sampling time will be used for summary statistics and relevant median plots, whereas for individual participant plots by time, the actual PK sampling time will be used.

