### 2.3.2. Benefit Assessment

A single dose of PF-06882961 administered in this study is not expected to provide any clinical benefit to healthy participants or participants with hepatic impairment. This study is designed primarily to characterize the effect of varying degrees of hepatic impairment on the PK of PF-06882961. Results from this study will be used in conjunction with collective safety, efficacy, and PK/PD data from other PF-06882961 studies to provide recommendations on dosing for participants with varying degrees of hepatic impairment.

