### 3. OBJECTIVES AND ENDPOINTS

Objectives	Endpoints
Primary:	Primary:

To compare the PK of PF-06882961 following administration of a single oral dose in adult participants with varying degrees of hepatic impairment relative to age- and body weight-matched participants without hepatic impairment.

	

Plasma: <math>C_{max}</math>, <math>AUC_{inf}</math>, <math>AUC_{last}</math>, <math>fu</math> as data permit.

Secondary:	Secondary:

To evaluate the safety and tolerability of a single oral dose of PF-06882961 when administered to adult participants with varying degrees of hepatic impairment and in age- and body weight-matched participants without hepatic impairment.

	

Assessment of treatment emergent AEs, clinical laboratory abnormalities, vital signs, ECG parameters.

Tertiary/Exploratory:	Tertiary/Exploratory:

To compare additional PK parameters of PF-06882961 following administration of a single oral dose in adult participants with varying degrees of hepatic impairment and in age- and body weight-matched participants without hepatic impairment.

	

Plasma: <math>C_{max,u}</math>, <math>AUC_{inf,u}</math>, <math>AUC_{last,u}</math>, <math>CL/F</math>, <math>CL_u/F</math>, <math>V_z/F</math>, <math>V_{z,u}/F</math>, <math>T_{max}</math>, <math>t_{1/2}</math> as data permit.

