**Table 2. Expected Widths of the 90% CIs (with 80% Coverage Probability) for Different Possible Estimated Effects**

Estimated Effect (Test/Reference)	AUC inf	
	Probable 90% CI	Probable CI Width
75%	43% to 129%	86%
100%	58% to 172%	114%
150%	87% to 259%	172%
200%	116% to 345%	229%
400%	232% to 690%	458%

These estimates are based on an assumed conservative between-participant standard deviation of 0.489 (equivalent to a geometric coefficient of variation of 52%) for logeAUCinf (also applicable to logeCmax) based on data from 2 previous studies conducted in healthy volunteers with PF-06882961 administered as a single dose in the fed state (C3421001 & C3421003).

Participants who discontinue from the study before completing all assessments may be replaced at the discretion of the investigator and sponsor.

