3.3. Other Endpoint(s)

- Additional PF-06882961 Plasma Pharmacokinetic parameters: CL/F, V_z/F, T_{max}, t_{1/2} as data permit.
- Unbound PF-06882961 Plasma Pharmacokinetic parameters: C_{max,u}, AUC_{inf,u}, AUC_{last,u}, CL_u/F, V_{z,u}/F as data permit.

The plasma PK parameters for PF-06882961 in Table 4 will be determined using standard non-compartmental methods:

Table 4. Summary of Additional Plasma PK parameters of PF-06882961 to be calculated

Parameter	Analysis Scale	PF-06882961 20mg
-----------	----------------	------------------

CL/F*	ln	D
V _z /F*	ln	D
T _{max}	R	D
t _{1/2} *	R	D

*=if data permits. Abbreviations: D=displayed with descriptive statistics as outlined in Table 7 in Section 6.3; ln=natural-log transformed, R=raw (untransformed).

The plasma PK parameters for unbound PF-06882961 will be calculated as described in Table 5:

Table 5. Summary of Plasma PK parameters of Unbound PF-06882961 to be calculated

Parameter	Method of Determination	Analysis Scale	PF-06882961 20 mg
AUC _{last,u}	fu × AUC _{last}	ln	D
AUC _{inf,u} *	fu × AUC _{inf}	ln	D
C _{max,u}	fu × C _{max}	ln	D
CL _u /F*	Dose/(AUC _{inf,u})	ln	D
V _{z,u} /F*	Dose/(AUC _{inf,u} × k _{el})	ln	D

*=if data permits. Abbreviations: D=displayed with descriptive statistics as outlined in Table 7 in Section 6.3; ln=natural-log transformed, R=raw (untransformed).

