5.2.3. One-way Analysis of Variance (ANOVA)

The *one-way analysis of variance (ANOVA)* model will include group as a factor.

Estimates of the adjusted mean differences (Test - Reference), and corresponding 90% CIs, will be obtained from the model. These will be exponentiated to provide estimates of the ratio of adjusted geometric means (Test/Reference) and 90% CIs for the ratios. Example SAS code is given in [Appendix 1](#).

Additionally, as an exploratory analysis, age and body weight may be explored as an additional covariate in the models, as appropriate. This will be implemented by utilizing a stepwise linear regression approach, with model selection using Akaike's Information

Criterion [AIC]). All the above covariates will be considered (group as a factor will be restricted to always remain in the model) and if the final model selected includes at least one of these additional covariates, this additional model will be reported in addition to the main ANOVA model above. Example SAS code is given in [Appendix 1](#).

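### Unbound AUCinf, AUClast and Cmax are to be compared between cohorts, but no Test/Reference ratio or 90% CI is planned for them; adding them to the existing ANOVA costs almost nothing.

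*SAP*

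**What the plan says.** Protocol Section 3 and SAP 2.1 give the tertiary/exploratory objective as "To compare additional PK parameters of PF-06882961 following administration of a single oral dose in adult participants with varying degrees of hepatic impairment" and in matched participants without impairment. The endpoints listed for it include Cmax,u, AUCinf,u and AUClast,u.

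SAP 3.3, Table 5 ("Summary of Plasma PK parameters of Unbound PF-06882961 to be calculated") puts these three on the natural-log scale and gives them only the code D, defined as "D=displayed with descriptive statistics as outlined in Table 7 in Section 6.3". The primary parameters in SAP Table 3 are coded A and D, that is, modelled and described.

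SAP 6.3.1 says the additional parameters "will be listed and summarized descriptively by group in the PK parameter set (as defined in Section 4"). Table 7 adds summary statistics for each group, including N, geometric mean and geometric CV%. Box plots overlaid with geometric means are also planned.

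The model-based comparison in SAP 6.1.1.1 takes total Cmax, AUCinf, AUClast and fu, "for each of the hepatic impairment groups (Test, Groups 2, 3, 4) to the healthy normal hepatic function group (Reference, Group 1"). SAP 5.2.3 gives its output: "Estimates of the adjusted mean differences (Test - Reference), and corresponding 90% CIs, will be obtained from the model", then exponentiated to ratios. Protocol 9.4.1.2 draws the same line: ANOVA for the four primary parameters, plots and descriptive summaries for the unbound ones.

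**The concern.** The study measures the effect of hepatic impairment by a Test/Reference geometric mean ratio with a 90% CI. Unbound exposure, which the tertiary objective sets out to compare, is not given that measure in either document.

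The planned total-drug and fu ratios fill only half the gap. Their product gives the unbound point ratio if the same participants contribute to both. The two separate intervals cannot be combined into the unbound interval, because neither analysis reports the covariance between ln exposure and ln fu. A reader who multiplies the limits gets an interval that is too wide.

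The stake is modest. A change in binding would still show, since fu is a primary endpoint with its own ratio and CI. However, Protocol 2.3.2 says the results will be used "in conjunction with collective safety, efficacy, and PK/PD data from other PF-06882961 studies to provide recommendations on dosing" in hepatic impairment. A planned interval for unbound exposure, reported beside the total-drug and fu intervals, is easier to use there than one rebuilt later.

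**Working it through.** **Inputs from the documents.** Between-participant SD of ln AUCinf is 0.489, also applied to ln Cmax (Protocol 9.2). There are 6 participants in each of 4 cohorts, so the residual df are 24 - 4 = 20. Intervals are 90%. Protocol Table 2 ("Expected Widths of the 90% CIs (with 80% Coverage Probability) for Different Possible Estimated Effects") also uses an 80% coverage probability.

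**Inputs assumed.** The documents as read give no SD of ln fu (call it s) and no correlation of ln fu with ln AUC (call it r). I take s = 0.25 with r from -0.7 to +0.3, then vary s.

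**Reproducing Table 2.** Log half-width = t(0.95, 20) × SD × sqrt(1/6 + 1/6) × sqrt(chi2(0.80, 20)/20).

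- t = 1.7247 and the coverage factor is 1.1189.
- Without the coverage factor: 1.7247 × 0.489 × 0.5774 = 0.487, a multiplier of exp(0.487) = 1.63.
- With it: 0.487 × 1.1189 = 0.545, a multiplier of 1.724.
- At 100% this gives 58%-172%, and at 200% it gives 116%-345%. All five printed rows are matched.

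**Unbound AUC.** Since AUCu = fu × AUC, ln AUCu = ln AUC + ln fu. Hence SD(ln AUCu) = sqrt(0.489² + s² + 2 × r × 0.489 × s). With s = 0.25:

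| r | SD(ln AUCu) | Multiplier | Multiplier, 80% coverage | 90% CI at a 200% ratio, 80% coverage |
|---|---|---|---|---|
| -0.7 | 0.361 | 1.43 | 1.50 | 134%-299% |
| -0.3 | 0.478 | 1.61 | 1.70 | 117%-341% |
| 0 | 0.549 | 1.73 | 1.84 | 108%-369% |
| +0.3 | 0.612 | 1.84 | 1.98 | 101%-396% |
| Total AUC (Table 2) | 0.489 | 1.63 | 1.72 | 116%-345% |

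Over the same range of r, the multiplier with coverage runs from 1.56 to 1.85 for s = 0.15 and from 1.48 to 2.23 for s = 0.40.

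**Multiplying the separate limits.** For fu alone with s = 0.25 the multiplier is 1.28 (1.32 with coverage). The product with the total-drug multiplier is 1.627 × 1.283 = 2.09 (2.28 with coverage), wider than every unbound row above. A simulation of 20,000 trials for each correlation (s = 0.2; r = -0.5, 0, +0.5) agrees. The ANOVA on unbound AUC covered the true ratio 89.8%, 90.3% and 89.8% of the time, and the multiplied limits 99.2%, 97.0% and 93.4%. The unbound point ratio equalled the product of the total and fu ratios to rounding error.

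**Rebuilding from SAP Table 7.** The log SD in each group is sqrt(ln(1 + CV²)), with CV the geometric CV. Pooling the four group variances on their degrees of freedom gives the ANOVA residual variance, and the geometric means give the ratio. In 2,000 simulated data sets, with geometric means rounded to 4 significant figures and geometric CV to whole percent, the rebuilt 90% limits were always within 0.4% of the ANOVA limits.

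**The case against.** The strongest reply is that the plan is consistent and looks deliberate. Protocol 9.4.1.2 confines the ANOVA to the primary parameters and assigns the unbound ones to plots and descriptive summaries, and the SAP carries this through with explicit codes. To compare need not mean a ratio with an interval: geometric means by group permit a comparison, and SAP 5.1 plans no tests or decision rules that would depend on one. Other parameters under the same objective, such as t1/2 and Tmax, would stay descriptive after the change. The unbound interval can be rebuilt from Table 7, and individual values will be listed. The widths above rest on assumed fu variability. At s = 0.25 and a correlation of about -0.26, the unbound interval is exactly as wide as the total-drug one.

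Most of this stands. The two documents do not contradict each other, no information is lost, and the widths illustrate precision rather than measure harm. It does not remove the case for the change. The three unbound exposure parameters are the direct counterparts of the three total-drug exposure parameters already modelled, and they are already derived on the log scale. An interval each reader has to rebuild is a poor substitute for one that is planned and reported.

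**Conclusion.** The point holds as an inexpensive improvement to a tertiary analysis. It is not an error, and it does not threaten the primary analysis. No ratio or 90% CI is pre-specified for AUCinf,u, AUClast,u or Cmax,u, and the interval cannot be formed from the planned total-drug and fu intervals.

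Unbound precision could be better or worse than that shown for total drug in Table 2: a multiplier of 1.50 to 1.98 against 1.72 for s = 0.25 and correlations from -0.7 to +0.3, with 6 participants per cohort. These figures depend on the assumed s and correlation. If Cohort 4 has only the 4 participants the protocol allows, with 6 in Cohort 1 (18 df), the interval is wider: 108%-370% at a 200% ratio even if the unbound SD were 0.489.

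**What to change.** In SAP Table 5, change the code for AUCinf,u, AUClast,u and Cmax,u from D to A and D, with the code A defined in the footnote as in Table 3. In SAP 6.3.1, state that the one-way ANOVA of Section 5.2.3, with all four groups in one model, will be applied to their natural logs. Report the Test/Reference geometric mean ratios and 90% CIs beside the total-drug and fu ratios.

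Keep the three as tertiary/exploratory endpoints and apply the rules of SAP 5.3.1 for parameters that cannot be calculated or are known to be biased. Unbound CL/F needs no model of its own: at one fixed dose its ratio is the reciprocal of the AUCinf,u ratio.

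The cost is a few words in the SAP and three more runs of an existing model. No new data, samples or participants are needed. No multiplicity question arises, because nothing is tested. SAP Section 2 calls for a protocol amendment only for major changes to the primary endpoint or its analysis, so none is required here.
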